## **Study Design and Methods**

### **I. Subjects:**

#### **A. Overview:**

The proposed study will comprise of two parts: Part I: an observational study based on ecological momentary assessment, and Part II: a randomized partial crossover clinical trial. Same subjects will participate in both parts of the study.

In the observational study, the dietary intake of the subjects will be evaluated using an ecological momentary assessment approach for 7 days. In the randomized partial crossover clinical trial, four test breakfasts will be administered so that each subject will get exposed to only two out of the four diets (thus, partial crossover). Therefore, there will be six possible combinations of diets (i.e.  $4! / 2! [4-2]!$ ) and 12 possible ordered combinations (i.e. permutations;  $4! / [4-2]!$ ) of diets. Four subjects will be randomly assigned to each of these 12 possible ordered combinations of diets. Thus, the total sample size will be 48 (i.e.  $n = 4 \times 12$ ).

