### **E. Blood work**

To collect blood samples, an IV catheter will be placed in the subject's upper limb by a registered nurse. Hence, there will be one needle stick per visit. If an adequate blood sample cannot be accessed using the IV catheter, which happens rarely, with the subject's approval, a singlestick needle blood withdrawal will be performed. However, there will be total of 4 needle sticks including the initial needle stick done to insert the IV catheter applied in a single visit. The recruited registered nurse is an experienced person who is currently working in the ER. She is properly trained in placing IV catheters and drawing blood. A total of 20 mL (4 teaspoons/ 1.3 tablespoons ) of blood will be taken at all pre-and postprandial blood draws, which will be used to assess the levels of hormones via radioimmunoassay kit, blood glucose levels and HbA1c. Blood will be drawn into chilled EDTA tubes (Greiner Vacuette, Monroe, NC) and immediately spun at 1600 x g for 15 minutes at 4°C. Aprotinin (0.6TIU/ml, Phoenix Pharmaceuticals Inc, Burlingame, CA) will be immediately added to the plasma which then will be aliquoted and stored at -80 degrees until assayed for HbA1C, ghrelin, PYY3-36, GLP-1 and insulin. For blood glucose levels, samples will be collected for sodium fluoride containing EDTA tubes (Greiner Vacuette, Monroe, NC). Blood draws will be continuously done at 30 minutes before and 30, 60, 90, 120 and 180 minutes after breakfast consumption. The room has been designed to conduct blood draws.

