#### **I. Food Record and 24-hour Recall**

Food record will be maintained by each subject for 7-day period (Appendix G). A 24-hour recall will be collected on the day 1 of the 7 days using Automated Self-Administered 24-Hour (ASA24®) Dietary Assessment Tool.

**Visit 1-** The eligible subjects will come to TTU clinic (Tech Plaza rooms 302 and 305) at about 8 AM after 10 hours fast. Here subjects are allowed to take water. After obtaining informed written consent (Appendix C), anthropometric measurements like weight, height, waist and hip circumferences and blood pressure measurements will be taken (Table 4).

Next, pre-prandial blood sampling will be down 30 minutes prior to test breakfast 1. To retrieve blood samples, an IV catheter will be placed by the registered nurse. Blood draws will be continuously done at 30 before and 30, 60, 90, 120, and 180 minutes after breakfast consumption. Pre-prandial blood draw will be done to assess fasting blood glucose, HbA1c, and hormone levels (i.e. serum insulin PYY, GLP1, ghrelin). Post-prandial blood draws will be done to assess blood glucose and hormone levels. Following pre-prandial blood draw, subjects will be asked to assess their hunger and fullness using the visual analog scale (VAS) (Appendix E). The RMR will be tested for each subject, followed by a standardized test breakfast 1, provided a smartphone and trained to photograph their food intake, using the smartphone provided. The subjects will be asked to consume the entire breakfast in 10 minutes. A food frequency

questionnaire (FFQ) (Appendix F) will be given to assess the egg consumption. RMR will be determined 60 and 120 min post breakfast. Blood draws and VAS administration will be continuously done at 30, 60, 90, 120 and 180 minutes after breakfast consumption. After testing is complete at the 180-minute post-breakfast mark, the subject's IV catheter will be removed.

Subjects will take photos of foods before eating and of the leftovers if any with the help of a smartphone using SmartIntake© app for 7-days. Participants will record all meals for the next 7 days in a food record (Appendix G) as well. On the following day (day 1 of 7 days) a 24-hour recall will be done using Automated Self-Administered 24-Hour (ASA24®) Dietary Assessment Tool.

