**Visit 2-** On day 8, participants will be asked to return with 10 hours fast. As in Visit 1, an IV catheter will be placed by the registered nurse in the subject's upper limb to collect blood for blood glucose, and hormones. Blood will be collected for fasting blood glucose levels and insulin levels PYY, GLP1, ghrelin (as described above) 30 minutes prior to the breakfast. They will be randomized to receive test breakfast 2. Blood draws will be continuously done at 30, 60, 90, 120 and 180 minutes after breakfast consumption. Following each blood draw, subjects will be asked to assess their hunger and fullness using the visual analog scale (VAS) (Appendix E). RMR will be determined 30 mins prior and 60 and 120 min post breakfast.

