### **Outcome Measures:**

#### **A. Primary Outcome Measures:**

1. Difference of energy intake (kcal) in meals containing eggs as compared to meals that do not contain eggs

Energy intake will be determined using Remote Food Photography Method (RFPM) and the meals of all test subjects will be categorized based on the presence or the absence of eggs in the meals.

[Time Frame: Day 1-7 of the ecological momentary assessment part (Part I) of the study]

2. Difference of energy intake (kcal) in high egg consumers as compared to low egg consumers  
Comparison of mean daily energy intake as measured by Remote Food Photography Method (RFPM) between high egg consumers and low egg consumers identified by providing a food frequency questionnaire (FFQ).

[Time Frame: Day 1-7 of the ecological momentary assessment part (Part I) of the study]

3. Difference of saturated fat (g) intake in meals containing eggs as compared to meals that do not contain eggs

Saturated fat intake will be determined using Remote Food Photography Method (RFPM) and the meals of all test subjects will be categorized based on the presence or the absence of eggs in the meals.

[Time Frame: Day 1-7 of the ecological momentary assessment part (Part I) of the study]

4. Difference of saturated fat (g) intake in high egg consumers as compared to low egg consumers

Comparison of saturated fat intake as measured by Remote Food Photography Method (RFPM) between high egg consumers and low egg consumers identified by providing a food frequency questionnaire (FFQ).

[Time Frame: Day 1-7 of the ecological momentary assessment part (Part I) of the study]

5. Difference of blood glucose levels compared between different test breakfasts

This will be measured on visit 1 and 2 after providing test breakfasts.

[Time Frame: Changes in concentration (area under the curve; AUC) from 30 minutes prior to breakfast to 180 minutes after consumption of test breakfasts (Part II of the study)]

6. Difference of insulin levels compared between different test breakfasts

This will be measured on visit 1 and 2 after providing test breakfasts.

[Time Frame: Changes in concentration (area under the curve; AUC) from 30 minutes prior to breakfast to 180 minutes after consumption of test breakfasts (Part II of the study)]

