**Statistical Analyses Plan (SAP):**

Data will be imported to R statistical software and the distributions will be examined visually to make a decision about the appropriate statistical tests (i.e. parametric / non-parametric) to be used for all comparisons. All statistical analyses will be conducted using R statistical software. Family-wise error rate will be maintained at 0.05.

Free living EI and saturated fat intake during main three meals (i.e. breakfast, lunch and dinner) of each subject will be determined using RFPM and the meals of all test subjects will be categorized based on the presence or the absence of eggs in the meals. Means of EI and saturated fat intake during each main meal will be compared between the two categories (i.e. eggs present vs. eggs absent) using multi-level mixed-effects regression models constructed using the lmerTest package in R statistical software. Age, sex, baseline BMI and / or waist circumference will be included in the models as subject-level covariates.

Based on RFPM data, mean EI and saturated fat intake of the high egg consumers (i.e. individuals in the top quartile based on egg consumption) will be compared with the mean EI and saturated fat intake of the low egg consumers (i.e. individuals in the bottom quartile based on egg consumption) via Welch t-tests or the Wilcoxon test, depending on the distributions of the data.

Linear regression models will be constructed to examined the associations between a) total EI, b) saturated fat intake and c) egg intake and each of i) baseline insulin level, ii) blood glucose level, iii) HOMA-IR, and iv) HbA1C level. The usual regression assumptions will be assessed and any concerns will be ameliorated as appropriate (e.g. apply a transformation as guided by Box-Cox)

Using the data obtained in the randomized partial crossover trial, multi-level mixed effects regression models will be constructed using the lmerTest package in R statistical software to predict each of a) PYY (AUC and pre-post change); b) GLP-1 (AUC and pre-post change); c) ghrelin (AUC and pre-post change); d) blood glucose (AUC and pre-post change); e) insulin (AUC and pre-post change); f) metabolic rate using i) the presence of eggs in the diet; ii) the

presence of a high content of saturated fat in the diet; iii) their interaction. Age, sex, baseline BMI and / or waist circumference will be included in the models as subject-level covariates.

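### The Part II models omit visit and the same-visit fasting value, both already recorded, so glucose, insulin and hormone comparisons may be reported with less precision than the data allow

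*Combined protocol and SAP*

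**What the plan says.** The Statistical Analyses Plan fits multi-level mixed-effects models to the Part II data. The outcomes are PYY, GLP-1 and ghrelin, each as AUC and pre-post change, then "d) blood glucose (AUC and pre-post change); e) insulin (AUC and pre-post change); f) metabolic rate". The predictors are eggs, high saturated fat and "iii) their interaction. Age, sex, baseline BMI and / or waist circumference will be included in the models as subject-level covariates". Visit and the fasting value of the outcome are not listed there or elsewhere. The same section leaves to visual inspection the "appropriate statistical tests (i.e. parametric / non-parametric) to be used for all comparisons".

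Both missing variables are collected:

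- **Visit.** Under Overview, "Four subjects will be randomly assigned to each of these 12 possible ordered combinations of diets". The data collection sheet (Appendix D) has a visit-number field.
- **Fasting value.** Under Blood work, "Blood draws will be continuously done at 30 minutes before and 30, 60, 90, 120 and 180 minutes after breakfast consumption". For visit 1, "Pre-prandial blood draw will be done to assess fasting blood glucose, HbA1c, and hormone levels". For visit 2, "Blood will be collected for fasting blood glucose levels and insulin levels PYY, GLP1, ghrelin (as described above) 30 minutes prior to the breakfast".

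Primary outcomes 5 and 6 are glucose and insulin, described as "Changes in concentration (area under the curve; AUC) from 30 minutes prior to breakfast to 180 minutes after consumption of test breakfasts". Whether this AUC is total or incremental is not stated.

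**The concern.** In a crossover, the breakfast comparison draws mainly on differences between a subject's two visits. The listed covariates (age, sex, baseline BMI, waist) are subject-level, so they cannot reduce visit-to-visit noise. The two omitted variables vary between visits and could.

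The plan does use the fasting value, but only in fixed ways: pre-post change sets its coefficient at 1, and the AUC window includes the sample. Neither estimates the coefficient from the data.

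At stake are two primary outcomes and the egg-by-fat interaction of hypothesis 7. Each subject receives only two of the four breakfasts, and the 48 comes from the number of sequences rather than from a Part II power calculation. The only power statement in the file belongs to the 40-subject observational plan.

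**Working it through.** **Design.** 4!/(4-2)! = 12 ordered pairs; 12 x 4 = 48 subjects and 96 subject-visits, as the plan states. Each breakfast comes first in 3 pairs and second in 3, so it falls 3 x 4 = 12 times at each visit. Visit is therefore orthogonal to eggs, fat and their interaction when data are complete, and omitting it causes no bias.

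**The plan's power figures.** A paired t-test with n = 40, two-sided 0.05 and 80% power gives a detectable effect of 0.454 (stated 0.45); Fisher's z gives a correlation of 0.431 (stated 0.43). Neither concerns Part II.

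**Assumptions (not in the documents).** Subject random intercept; subject SD = within-subject SD = 1; visit shift d in within-subject SDs; within-subject correlation rho between fasting value and outcome.

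**Omitting visit.** For the within-subject part, reported SE is inflated by sqrt(1 + d²/2): 1.6% at d = 0.25, 6.1% at 0.5, 22.5% at 1. The full model also uses between-subject information, so its inflation is slightly smaller. REML simulation of the 12 x 4 x 2 design (2,000 runs per setting, rho = 0.5) gave, for the average egg effect:

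| d | Planned SE (true SD) | + visit SE (true SD) | Reported-SE inflation |
|---|---|---|---|
| 0 | 0.230 (0.240) | 0.230 (0.240) | 0% |
| 0.25 | 0.232 (0.233) | 0.229 (0.233) | 1% |
| 0.5 | 0.243 (0.230) | 0.231 (0.229) | 5% |
| 1 | 0.275 (0.239) | 0.231 (0.235) | 19% |

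True sampling SD hardly moves. The planned test becomes conservative: type I error 4.3% at d = 0.5 and 3.1% at d = 1.

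**Omitting the fasting value.** Within-subject variance falls by about rho² when it is added. Simulation at d = 0, with visit added and fasting split into subject mean and within-subject deviation; equivalent n = 48 x (true SD after / true SD planned)²:

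| rho | Planned SE (true SD) | Both terms SE (true SD) | Change in SE | Equivalent n |
|---|---|---|---|---|
| 0 | 0.230 (0.228) | 0.232 (0.230) | +1% | 49 |
| 0.3 | 0.231 (0.241) | 0.223 (0.233) | -4% | 45 |
| 0.5 | 0.230 (0.240) | 0.202 (0.212) | -12% | 37 |
| 0.7 | 0.229 (0.228) | 0.166 (0.167) | -28% | 26 |

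For example, 48 x (0.212/0.240)² = 37: at rho = 0.5, the planned 48 subjects give the precision that about 37 would give with both terms. The interaction SE is about twice as large and falls in proportion, from 0.463 to 0.405 at rho = 0.5.

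**Power** for an assumed egg effect of 0.6 within-subject SD at nominal 0.05, planned / + visit / + visit and split fasting:

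- rho 0.5: 74/74/84% at d = 0; 70/74/84% at d = 0.5; 59/74/84% at d = 1.
- rho 0.3, d = 0: 75/75/78%.

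**Pre-post change.** With equal variances, the change score has variance 2(1-r) and the adjusted analysis 1-r², a ratio of (1+r)/2: 0.65, 0.75 and 0.85 at r = 0.3, 0.5 and 0.7.

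**AUC from the six protocol samples.** Trapezoid weights are 30, 45, 30, 30, 45, 30, totalling 210 minutes, so fasting carries 30/210 = 14.3% of total AUC. The SE ratio is about 1/sqrt(1 - c²), where c is the correlation of the AUC with the fasting value. With equal SDs and common correlation 0.3:

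- variance = 7,650 + 0.3 x (210² - 7,650) = 18,585
- covariance with fasting = 30 + 0.3 x 180 = 84
- c² = 84²/18,585 = 0.38, a loss of about 27% (simulated 26%).

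Simulated excess of planned SE over the split model (800 runs per setting), for post-meal SD 1, 2 and 3 times fasting:

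| Correlation among samples | Total AUC | Net incremental AUC |
|---|---|---|
| Independent | 5%, 1%, 0% | 137%, 47%, 22% |
| 0.3 | 26%, 17%, 15% | 52%, 4%, -1% |
| 0.5 | 49%, 39%, 35% | 29%, -1%, 3% |

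Net incremental AUC is total AUC minus 210 x fasting. Once fasting is a covariate in a linear model, both therefore give the same breakfast estimates and SEs on the raw scale.

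**The case against.** The planned model is a coherent analysis of a randomized crossover: its contrasts are unbiased and, with complete data, its tests hold their level. Better covariates are a refinement. Four points carry weight.

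- Visit affects only the reported SE. The large figures need a shift of a full within-subject SD, and nothing in the documents suggests one that large, since both visits use the same 10-hour fast and sampling schedule. This stands, though seven days of photographing and recording food between visits make some shift plausible.
- The fasting value is already used in pre-post change, and the primary-outcome wording can be read as baseline-referenced AUC. On that reading, with post-meal SD two or three times fasting and correlated samples, the gain is close to nil. This stands for those settings. Total AUC fits the text equally well, and there the loss is 15% to 49% in the correlated settings.
- The relevant correlation is between visit-to-visit deviations, because the random intercept already absorbs stable differences. The documents say nothing about its size. This stands; at 0.3 the gain is modest.
- The mean/deviation split helps only when between- and within-subject slopes differ. Otherwise a single slope does marginally better (SE 0.201 against 0.202 at rho 0.5). This stands, so the split is a preference.

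None of this removes the case for the change: the possible loss is about 1% in SE, and the possible gain falls on primary outcomes. Deciding on adjustment after seeing the data would add an analyst choice to those the SAP already leaves open.

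**Conclusion.** The point holds as a matter of precision and power; there is no bias. The Part II models omit two recorded variables. Depending on inputs the documents do not give, the reported SE of the egg effect is 0% to 19% too large for want of visit (shift 0 to 1 within-subject SD). Adding both terms with no visit shift changes the SE by between about +1% and -28% (correlation 0 to 0.7). For some incremental-AUC settings the gain is nil.

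The figures assume a subject random intercept, complete data, normal errors and equal subject and within-subject SDs. Dropout would break the visit balance. The power figures are at nominal 0.05; family-wise control would lower all of them. The change is worth making before analysis, with medium confidence in the size of its benefit.

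**What to change.** In the SAP paragraph on the partial crossover, for glucose, insulin, PYY, GLP-1 and ghrelin:

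1. Add visit (1/2) as a fixed effect.
2. Add the same-visit value of the outcome at -30 minutes as a covariate, preferably as subject mean plus within-subject deviation. Keep a subject random intercept, stated explicitly, and the listed covariates.
3. State whether AUC is total or net incremental. With item 2 the choice does not alter the raw-scale breakfast estimates, but it does matter after a transformation (an assumed log-scale example gave egg effects of 0.192 and 0.245) or with a non-parametric test, both of which the SAP leaves open.

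Metabolic rate is outside this change. Table 3 marks RMR at visit 1 only, while the Visit 2 text and secondary outcome 8 place it at both visits; those passages must be reconciled first.

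The cost is two or three sentences, three model degrees of freedom and at worst about 1% in SE. No new data are needed.

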## **B. Hypotheses:**

These aims will test the following hypotheses:

1. Meals that include eggs will have higher energy and saturated fat contents as determined by RFPM, compared to corresponding meals (i.e. breakfast, lunch, or dinner) without eggs.
2. As determined by RFPM, individuals of the study sample who will be in the highest quartile in terms of egg consumption in the free-living condition (defined as high egg consumers) will have a higher intake of saturated fat and total energy as compared to individuals who will be in the lowest quartile in terms of egg consumption (defined as low egg consumers).
3. Baseline insulin level, blood glucose level, the Homeostatic Model Assessment (HOMA) index of insulin resistance using fasting glucose and insulin levels, and HbA1C will be positively associated with total EI and saturated fat intake determined by RFPM, even when adjusted for age, sex, BMI and waist circumference
4. Above outcome variables will not be associated with egg intake determined by RFPM.

5. In the randomized partial crossover study, presence of eggs in the breakfast will be associated with a) a greater increase (i.e. both area under the curve and pre-post change) in satiety hormones (i.e. PYY and GLP-1), b) a less profound increase in blood glucose and insulin levels, c) a greater decrease in the hunger hormone (ghrelin) and d) an increase in the area under the curve of metabolic rate when controlled for the content of saturated fat in the test diets.
6. In the randomized partial crossover study, presence of a high amount of saturated fat in the breakfast will be associated with a) a greater increase (i.e. both area under the curve and pre-post change) in satiety hormones (i.e. PYY and GLP-1), b) a less profound increase in blood glucose and insulin levels, c) a greater decrease in the hunger hormone (ghrelin) and d) an increase in the area under the curve of metabolic rate when controlled for the presence of eggs in the test diets.
7. In the randomized partial crossover study, the associations mentioned in hypothesis 5 will be moderated by the presence of a high amount of saturated fat in the diet.
8. Estimates of total EI by RFPM will be significantly greater than EI estimates by 7-day food record and the 24-hour recall in dietary assessment.

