### **C. Significance:**

An association between egg consumption and diabetes should not be ignored. However, it is important to identify if such an association does indeed exist and, if so, whether or not there is evidence that suggests that it is not the eggs themselves that drive the association, but rather a concurrent undesirable profile of macronutrient intake. Food intake data assessed by subjective recall methods are highly questionable due to potential inaccuracies . Capturing food intake data in real time by RFPM is the greatest strength of this project. The RFPM has been validated for accuracy against the doubly labeled water method . With high accuracy, we will identify the nutrients associated with egg consumption. Intake at every meal will be captured for 7 days in a free-living population, which eliminates the reporting bias around subjective measures of food intake and provides greater fidelity of reporting usual diet. This will help in better understanding the health effects that are currently ascribed to eggs by epidemiological studies using dietary recall methods. We expect that this study will demonstrate that intake of eggs is associated with an undesirable profile of macronutrient intake. By doing measuring blood

glucose, insulin levels following four tests breakfast that include eggs and saturated fats we will be able to measure the acute effects of egg based diet and influence of saturated fats to glycemic status. In addition, by doing hunger and satiety hormones will enable to explain the changes that coexist with insulin and glucose alterations. RMR will give indirect measurement of fed state. Overall, the studies will provide stronger evidence to accept or refute some of the adverse effects reportedly associated with egg consumption, so that appropriate dietary recommendations could be designed. It will form the basis for future research to determine if the dietary pattern accompanying eggs and not eggs per se is linked to diabetes and other adverse metabolic consequences.

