8. Difference in Resting Metabolic Rate (RMR) compared between different test breakfasts  
RMR will be assessed following different test breakfasts on visit 1 and 2.

[Time Frame: Changes in RMR (kcal/24hrs) on visit 1 and 2 following each test breakfast (Part II of the study)]

9. Difference in total energy intake (kcal) compared between Remote Food Photography Method (RFPM), 7-day food record and 24-hour recall

Comparison of mean energy intake as determined by RFPM with mean energy intake determined by 7-day food record and a single 24-hour recall.

[Time Frame: Day 1-7 of the ecological momentary assessment part (Part I) of the study]

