Mean EI estimates of food records and 24-hour recall methods will be compared with the EI estimates of RFPM both with and without controlling for age, sex, baseline BMI and / or waist circumference by constructing a mixed-effects regression model to predict EI using the lmerTest package in R statistical software. The methods of estimation will be included in the model as a categorical independent variable and RFPM will be specified as the reference category. Age, sex, baseline BMI and / or waist circumference will be included in the models as subject-level covariates.

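### The energy-intake method comparison leaves row unit and variance structure open; on its likeliest reading, one pooled standard error serves two contrasts of very different precision

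*Combined protocol and SAP*

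**What the plan says.** Hypothesis 8 makes two claims: "Estimates of total EI by RFPM will be significantly greater than EI estimates by 7-day food record and the 24-hour recall in dietary assessment". Secondary outcome 9 names the inputs: "Comparison of mean energy intake as determined by RFPM with mean energy intake determined by 7-day food record and a single 24-hour recall". Under Food Record and 24-hour Recall, and in the Visit 1 description, the photographs and the food record run over the same seven days, and the recall is done once, on day 1.

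The last paragraph of the SAP gives the analysis. "Mean EI estimates of food records and 24-hour recall methods will be compared with the EI estimates of RFPM", with and without covariates, by "constructing a mixed-effects regression model to predict EI using the lmerTest package in R statistical software". On the method term it says: "The methods of estimation will be included in the model as a categorical independent variable and RFPM will be specified as the reference category".

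The SAP does not say whether a row is a subject's mean or a daily value, which random effects are fitted, or whether residual variance may differ by method. The sentence on checking regression assumptions belongs to the regressions on glycaemic markers and is not repeated here.

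**The concern.** The three measurements differ in precision by design. Day-to-day variation in eating is common to RFPM and the food record and cancels in their difference. It does not cancel between a 7-day mean and a single day. A model with a subject intercept and one residual variance, which is what lmerTest fits by default, has no term for this.

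Hypothesis 8 rests on these two contrasts. If they share one standard error, the sharper contrast (RFPM-record) is judged against noise that belongs to the other and can miss a real difference. The noisier contrast (RFPM-recall) is judged too leniently.

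**Working it through.** **Stated figure.** The documents give no standard error, variance or power for outcome 9, so there is nothing to reproduce. The attached grant text gives 80% power for an effect size of 0.45 with 40 subjects. That agrees with a two-sided paired t-test (79.3%), but it was not set for this comparison.

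**Inputs from the documents.** n = 48 ("Thus, the total sample size will be 48"); 7 days of RFPM, 7 days of record, 1 day of recall. The SAP says "Family-wise error rate will be maintained at 0.05" but gives no split for outcome 9, so two-sided 0.05 per contrast is assumed.

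**Formula for one mean per method.** Let D12, D13 and D23 be the variances of the within-subject differences (1 = RFPM, 2 = record, 3 = recall).

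- Correct variance of a contrast: Dij/n.
- Variance from the random-intercept, common-variance model, for every contrast: (D12 + D13 + D23)/(3n).

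Age, sex, BMI and waist circumference are subject-level covariates. With complete data they do not change these within-subject contrasts.

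**Worked example. All SDs are assumptions, in kcal:** day-to-day 600; person-level method deviation 150/200/250 and daily method error 150/250/300 for RFPM/record/recall.

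- D12 = 150² + 200² + (150² + 250²)/7 = 62,500 + 12,143 = 74,643.
- D13 = 150² + 250² + 600²·f + 150²/7 + 300² = 178,214 + 360,000·f.
- D23 = 200² + 250² + 600²·f + 250²/7 + 300² = 201,429 + 360,000·f.

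Here f = 1 + 1/7 if the recalled day lies outside the seven photographed days, and 1 − 1/7 if it lies inside.

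| | Recall day outside | Recall day inside |
|---|---|---|
| D13 | 589,643 | 486,786 |
| D23 | 612,857 | 510,000 |
| Model SE, both contrasts | √(1,277,143/144) = 94 | √(1,071,429/144) = 86 |
| Correct SE, RFPM-record | √(74,643/48) = 39 | 39 |
| Correct SE, RFPM-recall | √(589,643/48) = 111 | √(486,786/48) = 101 |
| Model/correct, record | 94.2/39.4 = 2.4 | 86.3/39.4 = 2.2 |
| Model/correct, recall | 94.2/110.8 = 0.85 | 86.3/100.7 = 0.86 |

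Simulation agrees: correct SEs of about 40 (record) and 100-113 (recall). Power for a true 150 kcal RFPM-record difference is about 20% (outside) to 34% (inside) by the pooled model and 96% by a paired test. The false-positive rate for recall is just under 10%. Over day-to-day SDs of 400 to 800 and both timings, pooled-model power runs from 59% down to 4%, paired power stays at 96-97%, and the recall false-positive rate is 8-11%.

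**How far this depends on the assumptions.** In a grid with day-to-day SD 400-800, daily error SD 200, RFPM person-level SD 100 and record/recall person-level SD 0-600 (correlation 0-1), the record ratio runs from 0.99 to 4.36. It exceeds 2 when person-specific bias is small (SD 100 or less) and is about 1.0-1.5 when it is large (SD 600). The recall ratio runs from 0.82 to 1.05, with type I error 3.7-10.4%. If D13 = D23, the recall ratio cannot fall below √(2/3) = 0.816. In random draws over wide assumed ranges, the record SE was too large in 98% (median ratio 1.65; above 2 in 33%) and the recall SE too small in 89% (median ratio 0.86).

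**If daily rows are entered instead (7 + 7 + 1 per subject, random intercept only).** The model variances are σ²(1/7 + 1/7)/n and σ²(1/7 + 1)/n, so the two SEs are locked in the ratio √(8/2) = 2 whatever the data show. In the example the correct ratio is 110.8/39.4 = 2.8 or 100.7/39.4 = 2.6. Ignoring same-day pairing inflates the record SE; treating seven days as independent replicates of a person's reporting bias deflates it. With the example's inputs and day-to-day SD 400-800, the record SE ratio is about 0.9 to 1.6, power for 150 kcal is about 98% falling to 76%, and the recall false-positive rate is 5-11%. Other assumed biases give a record ratio as low as 0.63 and a recall ratio as high as 1.21.

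**The case against.** The strongest reply is that the SAP names a class of model, not a specific one. It fixes no row unit, random effects or residual structure, and its reference to mean intake may describe the contrast rather than the rows; the SAP uses similar words for its meal-level model. This stands in part. A reader might infer that the plan commits the trial to wrong error bars in known directions, or that the RFPM-record contrast loses most of its power in any case. The documents do not support either inference. The directions and the severe power loss belong to one-mean-per-method rows; with daily rows power is largely kept and either error can change sign.

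A reader might also take the recall figures to be independent of which day is recalled. They are not: the table differs by timing, and a recall done on day 1 could cover a day inside or outside the seven. The conclusion holds under both.

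All kcal inputs are assumed, and if person-specific reporting bias is large the record inflation is modest. The recall distortion is limited in any case.

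Finally, this is the last of nine secondary outcomes and touches no primary outcome or randomised comparison. On the favoured reading the record contrast errs on the conservative side. That limits the weight of the point but does not answer it, because neither row layout gives generally calibrated standard errors.

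**Conclusion.** The concern holds in a qualified form. The SAP puts two 7-day measures of the same week and one single-day measure into one lmerTest model without stating the row unit or allowing for their different precision.

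On the reading its wording favours, both hypothesis 8 contrasts get one pooled SE. The RFPM-record SE is then usually too large, typically about 1.5-2 times or more and less if reporting bias varies widely between people. The RFPM-recall SE is usually somewhat too small, with type I error up to about 10% instead of 5%. On daily rows the power loss is much smaller and the direction is not predictable, but miscalibration generally remains.

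The algebra follows from the design and the software default. The sizes in kcal and power rest on assumed variances. The sponsor should correct this before analysis, as a matter for a secondary outcome.

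**What to change.** Replace the single common-variance model for outcome 9 with two within-subject analyses: per-subject RFPM minus food record over the same days, and per-subject RFPM minus recall. Test each with a paired t-test, or with an intercept model on the difference, and report the mean difference with its confidence interval. If one model is preferred, use one row per method per subject with method-specific variances and an unstructured within-subject covariance (for example in nlme).

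In either case, state the unit of analysis, which day the recall covers, and which RFPM value it is compared with. Limits of agreement would be a useful addition but are optional.

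The cost is SAP wording and simple code; no new data are needed.
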